14 CENTRAL REVIEW PROCEDURES AND TISSUE COLLECTION

14.1 CTC Counts and Assessment of HER2 Status on CTCs

CTC counts and assessments of HER2 status are carried out by the laboratories named on page 3 of this protocol. For further information refer to section 2.2.

14.2 Tumor Tissue Sampling

If a biopsy of a metastatic site is carried out as part of the routine diagnostic work-up or a tumor block of the primary tumor is available, a sample of tumorous tissue will be investigated for further translational research.

15 STATISTICAL CONSIDERATIONS

15.1 Study Populations

The following study population sets will be examined:

Intention to Treat (ITT) Set: All recruited patients who received at least one dose of the study treatment (endocrine therapy plus everolimus/ribociclib or eribulin)

Safety Set: All recruited patients who received at least one dose of the study treatment and had at least one post-baseline safety assessment (the statement that a patient had no adverse events on the Adverse Event CRF is also regarded as a safety assessment). Patients who have received at least one dose of study treatment but who have no post-treatment safety data of any kind will be excluded from the safety set.

Per Protocol (PP) Set: All patients of the ITT set who did not violate any inclusion or exclusion criteria and who were treated according to protocol.

If necessary, further data sets required for additional analyses may be specified in separate analysis plans.

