1.2 Endpoints

1.2.1 Primary Endpoint:

Everolimus/Ribociclib cohort (DIVa)

CTC clearance rate: Proportion of patients with at least one CTC detected in 7.5 ml of peripheral blood drawn before treatment that show no evidence of CTCs in the blood after treatment (CTC prevalence as assessed using the Cell-Search® System; Veridex LLC, Raritan, USA).

Eribulin cohort (DIVb)

The primary endpoint is progression-free survival (PFS), defined as time interval from date of recruitment until progressive disease (PD) or death from any cause, whichever comes first (as defined by RECIST guideline version 1.1). If a patient has not had an event, progression-free survival is censored at the date of last adequate tumor assessment.

1.2.2 Secondary Endpoints:

In General

- Overall response rate (ORR): rate of complete (CR) and partial responses (PR) in patients in whom target lesions were defined
- Disease control rate (DCR): rate of patients who were assessed as having a PR or a CR or who had stable disease (SD) for at least 6 months
- Overall survival (OS), defined as the time interval from start of treatment until death due to any cause. If a patient is not known to have died, survival is censored at the date of last contact
- Dynamic of CTC: Descriptive statistics of regular CTC counts
- Level of compliance to the study protocol
- The assessment of safety will be based mainly on the frequency of adverse events. Other safety data (e.g. laboratory values, vital signs, and special tests) will be considered as appropriate
- Quality of life (QoL) as assessed by evaluation of the EORTC QLQ-C30 and EORTC QLQ-BR23 questionnaires
- Quality-adjusted survival (as assessed by the Q-TWiST method), with the utility scores for the different health states being prospectively determined in the clinical trial subjects based on the EORTC QOL C30 questionnaire

(CR, PR, and SD are defined according to the RECIST Version 1.1 criteria) (Eisenhauer 2009)

Everolimus/Ribociclib cohort (DIVa)	Eribulin cohort (DIVb)

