3.4.8 Pharmaceutical Data

Supply:

The investigator will prescribe eribulin according to the label. Any change of label will be communicated. The IMP Eribulin for all other patients not covered by the label will be provided by Eisai to the participating sites in the study setting and will be administered as i.v. injection at the study site. Eisai GmbH is responsible for shipment of the IMP eribulin to the clinical trial centers. Investigator's request of eribulin will be done through the eCRF (initial order automatically with recruitment, follow up orders as required).

Packaging:

5 ml type I glass vial, with teflon-coated, butyl rubber stopper and flip-off aluminium over seal, containing 2 ml of solution. The usual pack sizes are cartons of 6 vials, single vials will be available as well.

Labeling:

Packages will be signed with the warning "Zur klinischen Prüfung vorgesehen".

Stability:

Unopened vials are stable for 4 years when stored under the storage conditions described below.

Storage:

This medicinal product does not require any special storage conditions. From a microbiological point of view unless the method of opening precludes the risk of microbial contamination the product should be used immediately. If not used immediately eribulin as the undiluted solution in a syringe should not normally be stored longer than 4 hours at 25°C and ambient lighting, or 24 hours at 2°C - 8°C, in-use storage times and conditions are the responsibility of the user. Diluted solutions of eribulin (0.018 mg/ml to 0.18 mg/ml eribulin in sodium chloride 9 mg/ml (0.9%)) solution for injection should not be stored longer than 24 hours at 2°C - 8°C, unless dilution has taken place in controlled and validated aseptic conditions.

The storage temperature must be recorded weekly in the temperature log.

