- Review of the inclusion or exclusion criteria.
 - If during pre-treatment evaluation period a patient is found not to be eligible due to one of the inclusion or exclusion criteria, she is excluded from the study. Beyond the respective finding and the respective inclusion or exclusion criterion no further data need to be documented in the eCRF. Patients who are excluded from the study and who consent in additional assessment will be monitored during their course of disease as part of their routine treatment in order to gain further information about the impact of CTC detection on disease progression.
 - If the patient meets all inclusion criteria and none of the exclusion criteria, she is eligible according to section 7.0 of the protocol and for treatment according to section 8 of the protocol.
- Start of treatment according to the protocol / Dispense everolimus/ribociclib or eribulin to patients according to the treatment plan (section 8).
- Assessment of adverse events

Investigation		Time interval before re- recruitment
Blood Sampling with Screening Kit (Screening Visit) for CTC assessment	- Total number per 7,5 mL	3 weeks (Results must be available prior to IC part 2 and prior to start of Inclusion Visit)
	- HER2 status	
Hematology	- Hemoglobin - Hematocrit - Red blood cell count - Differential white blood cell count - Platelet count	7 days
Biochemistry	- Total and direct bilirubin - ALT - AST - Serum creatinine - Albumin - BUN or urea	7 days

	
 - Fasting cholesterol and triglycerides (Everolimus/ribociclib cohort only) - Fasting glucose (Everolimus cohort only) - Sodium, potassium, calcium(ribociclib-cohort only) - Potassium and Magnesium (Eribulin-cohort) 	
Pregnancy test	- (Eribulin cohort only)	7 days
Tumor evaluation (see section 10.2.1)	
 - Mandatory imaging - Other imaging as necessary to document all sites of disease - Clinical lesion status - Tumor markers (mandatory: CA15-3; optional: CEA, CA125) 	6 weeks
Cardiac investigations	- 12-lead ECG	3 weeks
Quality of life questionnaires	
 - EORTC QLQ-C30 - EORTC QLQ-BR23 	1 week

Table 12: Information on special investigations during Pre-Treatment Period

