10.1.2 Progression Free Survival (PFS)

PFS is defined as the time interval between the date of recruitment and the date of PD or death from any cause, whichever comes first.

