15.2 Statistical Methods

Statistical analysis of experimental data will be performed at the end of the studies, and there is no pre-planned interim analysis. For all parameters, descriptive statistics will be provided (absolute and relative frequencies for categorical data; number of valid and missing observations, means, standard deviations, medians, interquartiles, ranges, and confidence intervals – as appropriate – for continuous variables). Time-to-event data will be analysed using the Kaplan-Meier method and summarized using medians, 95% confidence limits, and Kaplan-Meier survival plots.

The analysis regarding the primary objectives will be based on the patients in the ITT set, with supportive analyses being conducted with the PP set. All other analyses regarding secondary objectives and endpoints will be performed based on the ITT set, the PP set, or subsets thereof, whatever is deemed appropriate.

The primary objective of the DETECT IV trial is to estimate treatment efficacy in patients with HER2-negative metastatic breast cancer and persisting exclusively HER2-negative circulating tumor cells; treatment efficacy will be assessed by the CTC clearance rate in patients treated with everolimus/ribociclib combined with endocrine therapy (everolimus/ribociclib cohort) or by progression-free survival (PFS) in patients treated with eribulin (eribulin cohort).

The everolimus/ribociclib cohort comprises postmenopausal patients with HER2-negative, hormone-receptor positive metastatic breast cancer with no indication for chemotherapy, and the eribulin cohort comprises both patients with HER2-negative, hormone-receptor positive metastatic breast cancer with indication for chemotherapy and patients with triple-negative metastatic breast cancer. There is no statistical hypothesis underlying the primary analysis. CTC clearance rate will be evaluated using non-parametric statistical methods appropriate for the analysis of frequencies and rates. PFS will be estimated using the Kaplan-Meier method, and median, 95% confidence limits and additional descriptive statistics as well as the Kaplan-Meier survival function will be presented. The effect of covariates on PFS will be evaluated using Cox regression models.

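### The set labelled ITT admits only dosed patients while eribulin-cohort PFS counts from recruitment, so any gap before the first dose biases PFS upward, probably slightly

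*Protocol*

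**What the plan says.** **Analysis set.** Protocol 15.1 defines the Intention to Treat set as "All recruited patients who received at least one dose of the study treatment". The Safety set also requires a dose, and the Per Protocol set is a subset of the ITT set. Section 15.2 states: "The analysis regarding the primary objectives will be based on the patients in the ITT set".

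**Time origin.** In section 1.2.1 PFS, the DIVb primary endpoint, is "defined as time interval from date of recruitment until progressive disease (PD) or death from any cause". Section 10.1.2 agrees: "PFS is defined as the time interval between the date of recruitment and the date of PD or death from any cause". New metastasis-free survival also counts from recruitment (1.2.2 and 10.1.6). Overall survival has two origins. Section 1.2.2 has "Overall survival (OS), defined as the time interval from start of treatment until death due to any cause", while section 10.1.3 starts the clock at recruitment.

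**From recruitment to first dose.** Section 6.3 lists, among the actions of the Inclusion/Recruitment Visit, "Start of treatment according to the protocol / Dispense everolimus/ribociclib or eribulin to patients according to the treatment plan". Sections 8.2.1.9 and 8.3.1.9 fix treatment Day 1 at that visit for everolimus and ribociclib; the eribulin instructions in 8.4.1.9 contain no such statement. Manufacturer-supplied eribulin is requested through the eCRF, with the "initial order automatically with recruitment, follow up orders as required" (3.4.8). Everolimus (3.2.9) and ribociclib (3.3.8) follow the same rule. On-label eribulin and everolimus with exemestane are prescribed by the investigator and do not depend on a shipment. The protocol gives no maximum interval from recruitment to first dose.

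**The concern.** An intention-to-treat set should be fixed at the time origin of the endpoint. Here the clock starts at recruitment, but membership is settled by a dose that may come later. If there is a gap, two things follow. Each dosed patient carries a stretch of follow-up in which a fatal event was impossible by construction, since a patient who died in it would not be in the set. And recruited patients who fail or leave before dosing vanish from the primary estimate. Both push PFS and new metastasis-free survival upward.

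The endpoint affected is the DIVb primary estimate, which is read against an assumed median of 3.7 months. In the everolimus/ribociclib cohort (DIVa) the primary endpoint is CTC clearance, so there only the missing undosed patients matter, not the guaranteed time.

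**Working it through.** **Inputs from the protocol**
- Median PFS 3.7 months; 120 enrolled, 10% loss; stated 95% interval width of about 1.3 to 1.5 months (15.3).
- Median overall survival on eribulin 13.1 months in the pivotal phase III trial (2.7.3).
- Tumor evaluation every 3 months (10.2.1).

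**Assumptions, not in the protocol**
- A recruitment-to-dose gap g of 7 or 14 days: 7/30.44 = 0.23 and 14/30.44 = 0.46 months.
- Constant hazards.
- All patients wait, unless stated otherwise.

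**Step 1: the plan's own figure.** 120 × 0.9 = 108. With all 108 having events under an exponential model, the interval is 3.7 × exp(±1.96/√108) = 3.06 to 4.47, a width of 1.40 months. This agrees with the stated width.

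**Step 2: ceiling.** Suppose every progression and death in the gap is detected and removed. The PFS hazard is ln 2/3.7 = 0.187 per month.
- Share removed, 1 − exp(−0.187g): 4.2% at 7 days and 8.3% at 14 days, about 5 and 10 of 120.
- Median from recruitment among those dosed, 3.7 + g: 3.93 and 4.16 months.
- Shift: +0.23 and +0.46 months, or 16% and 33% of the 1.40-month width.

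**Step 3: only deaths are lost.** With imaging every 3 months, a progression within a 7 to 14 day gap would rarely be found, so most such patients would still be dosed and stay in the set. The death hazard is ln 2/13.1 = 0.053 per month.
- Share removed, p = 1 − exp(−0.053g): 1.2% and 2.4%, about 1.5 and 3 of 120.
- Beyond the gap, survival in the dosed set is S(t)/(1 − p). Its median is 3.7 + g × 3.7/13.1 = 3.77 and 3.83 months.
- Shift: +0.07 and +0.13 months, or 5% and 9% of the width.

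**Step 4: not everyone waits.** If half the patients wait for shipped drug, the ceiling median falls to 3.81 months at 7 days and 3.93 at 14 days.

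**Step 5: no gap.** With g = 0 the shift is zero under either model.

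| Assumed gap | Only deaths lost | Ceiling, all wait | Ceiling, half wait |
|---|---|---|---|
| 0 days | 3.70 | 3.70 | 3.70 |
| 7 days | 3.77 | 3.93 | 3.81 |
| 14 days | 3.83 | 4.16 | 3.93 |

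Medians are in months from recruitment. Under this model, either aligned pairing (all recruited from recruitment, or dosed patients from first dose) returns 3.70.

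**The case against.** The best defence is that the protocol intends no gap. Treatment start belongs to the Inclusion/Recruitment Visit, that visit may extend over several days (6.3), and nothing excludes drug already held at the site. On-label eribulin needs no shipment. The trial is also non-randomised, with no hypothesis test, and its stated aim is to estimate efficacy in patients treated with eribulin, which a treated set addresses directly. Patients with a life expectancy under 3 months are excluded, so deaths before dosing should be few.

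Much of this stands, and it rules out several stronger readings that a reader might infer:
- That every analysed patient has waiting time. Patients on prescribed drug may start the same day.
- That patients on shipped drug cannot start on the day of recruitment. That is an inference which site stock would defeat; no delay is stated.
- That the expected bias is the ceiling in the working. The ceiling needs progressions to be detected between scans that are 3 months apart.
- That early-line and late-line results are distorted against each other. Section 15.2 plans exploratory PFS estimates by line and states no test between them. The label in 3.4.7 requires at least one prior regimen for advanced disease, so on that ground only first-line patients need shipped drug. Second-line patients in the same subgroup can be on label.

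The defence does not repair the definition. A treated set is a fair choice when time counts from first dose; here it is paired with a recruitment clock. An order sent with recruitment also sits badly with dosing at the recruitment visit, and no limit on the interval is set.

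**Conclusion.** The mismatch between the primary set and the PFS origin is plain in the text, and the ITT label is wrong for a set that requires a dose. A gap is plausible for patients on shipped drug, which in DIVb means those outside the label, but it is neither stated nor bounded. Any bias is upward. It is probably a small fraction of the planned interval width: 5% to 9% for an assumed 7 to 14 day wait in all patients when only deaths are lost, and less if only some patients wait. These figures rest on the assumed gap, constant hazards and a death rate borrowed from the pivotal trial. This is a minor point, worth correcting because the correction is cheap and removes the dependence on a gap whose length is unknown.

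**What to change.** - In 15.1, define the ITT set as all recruited patients for endpoints counted from recruitment (PFS and new metastasis-free survival). Keep the dosed set under its own name as a supportive analysis, with time counted from first dose.
- State one origin for overall survival in 1.2.2 and 10.1.3. Recruitment would match the corrected set.
- Reconcile the order rule in 3.2.9, 3.3.8 and 3.4.8 with the treatment start in 6.3, and record the dates of recruitment and first dose so that the gap can be reported. Placing the order before the eligibility review is a logistics question and is not needed for the analysis.

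**Cost.** Wording only, plus progression and survival status for undosed patients, which the end-of-study update for all patients in 8.6.2 should already cover. The downside is that a few never-treated patients enter the primary estimate. Those who withdraw undosed without a further scan would add almost no follow-up under the existing censoring rule.

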15.2 Statistical Methods

Statistical analysis of experimental data will be performed at the end of the studies, and there is no pre-planned interim analysis. For all parameters, descriptive statistics will be provided (absolute and relative frequencies for categorical data; number of valid and missing observations, means, standard deviations, medians, interquartiles, ranges, and confidence intervals – as appropriate – for continuous variables). Time-to-event data will be analysed using the Kaplan-Meier method and summarized using medians, 95% confidence limits, and Kaplan-Meier survival plots.

The analysis regarding the primary objectives will be based on the patients in the ITT set, with supportive analyses being conducted with the PP set. All other analyses regarding secondary objectives and endpoints will be performed based on the ITT set, the PP set, or subsets thereof, whatever is deemed appropriate.

The primary objective of the DETECT IV trial is to estimate treatment efficacy in patients with HER2-negative metastatic breast cancer and persisting exclusively HER2-negative circulating tumor cells; treatment efficacy will be assessed by the CTC clearance rate in patients treated with everolimus/ribociclib combined with endocrine therapy (everolimus/ribociclib cohort) or by progression-free survival (PFS) in patients treated with eribulin (eribulin cohort).

The everolimus/ribociclib cohort comprises postmenopausal patients with HER2-negative, hormone-receptor positive metastatic breast cancer with no indication for chemotherapy, and the eribulin cohort comprises both patients with HER2-negative, hormone-receptor positive metastatic breast cancer with indication for chemotherapy and patients with triple-negative metastatic breast cancer. There is no statistical hypothesis underlying the primary analysis. CTC clearance rate will be evaluated using non-parametric statistical methods appropriate for the analysis of frequencies and rates. PFS will be estimated using the Kaplan-Meier method, and median, 95% confidence limits and additional descriptive statistics as well as the Kaplan-Meier survival function will be presented. The effect of covariates on PFS will be evaluated using Cox regression models.

In the eribulin cohort, preplanned explorative subgroup analyses will be performed to evaluate PFS in the prospectively defined subgroups of hormone-receptor positive and triple-negative patients, as well as in the subgroups of patients receiving the first or second line of cytostatic treatment for metastatic breast cancer and patients receiving the third or fourth line of cytostatic treatment for metastatic breast cancer.

All analyses regarding the secondary objectives will have exploratory character only. The statistical methods described in the following section are appropriate for the data and distributions usually expected in this type of trials. The suitability of the statistical methods will be checked after data entry, and - if necessary - the methods will be modified accordingly.

The presence and number of circulating tumor cells (CTCs) measured at different time points will be evaluated in a descriptive way. The temporal changes in the number of CTCs will be described and analysed using appropriate generalized linear mixed models. In addition, different measures of CTC dynamics (based on various threshold values, relative or absolute changes in CTC counts) and their value for evaluating therapy efficacy or as a prognostic tool will be examined in detail by explorative data analyses.

All secondary endpoints and other outcomes that are calculated based on frequencies/rates (ORR, DCR, CR, PR, SD) will be summarized using frequency tables presenting absolute and relative frequencies together with appropriate confidence intervals. Comparisons between groups will be performed using suitable non-parametric statistical tests such as Fisher's exact test, χ^2 -test, or Cochran-Mantel-Haenszel test.

Overall survival will be estimated by the Kaplan Meier product limit method, and median values, 95% confidence intervals and survival plots will be provided. When appropriate, overall survival will be compared between groups using the logrank test, and additional multivariate analyses may be performed by suitable regression models (proportional hazard regression model, logistic regression).

Quality of life (QoL) will be assessed using the EORTC QLQ-C30 and BR23 questionnaires. The raw scores will be transformed to scores ranging from 0 to 100 following the instructions of the respective manuals. Descriptive statistics will be used to summarize both the single-item measures and multi-item scales at each scheduled assessment time point. Additionally, changes in QoL data between baseline scores and the scores obtained at the scheduled time points after start of the study treatment will be summarized for all patients with an evaluable baseline score and at least one evaluable post-baseline score. Longitudinal changes in QoL will be assessed using appropriate generalized linear mixed models with individual patients being fitted as random factors.

Unless otherwise noted, all statistical calculations will be implemented using the SPSS system (IBM Cooperation, New York, USA).

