
- Maximum duration of pre-treatment evaluation period (from screening to recruitment): 3 weeks
- Maximum duration of treatment period: 12 months
- Maximum duration of follow-up period: 24 months

Thus, the maximum duration of individual study participation is 36 months and 3 weeks.

Number of Clinical Trial Centers Planned to be Involved

A maximum of 100 clinical trial centers is planned to participate in the study.

Inclusion Criteria**In General for both study cohorts**

- Metastatic breast cancer, which cannot be cured by surgery or radiotherapy. The primary tumor and/or biopsies must have been confirmed as cancer by histopathology.
- HER2 status (as investigated on all primary tumor tissue and/or biopsies from metastatic sites or loco regional recurrences) must be negative. HER2-negativity is defined as (i.e.: immunohistochemistry (IHC) score 0-1+ or 2+ and fluorescent in situ hybridization (FISH) negative or just FISH negative, whichever was performed) in all tissue samples
- Evidence of CTCs. At least one CTC has been detected in 7.5 ml patient blood by means of the CellSearch® Circulating Tumor Cell Kit (Veridex LLC, Raritan, USA).
- HER2 negativity of all detected CTCs.
- Adequate organ function within 7 days before date of recruitment, evidenced by the following laboratory results:
 - absolute neutrophil count $\geq 1500/\mu\text{L}$
 - platelet count $\geq 100000/\mu\text{L}$
 - hemoglobin $\geq 9 \text{ g/dL}$
 - ALT (SGPT) $\leq 3.0 \times \text{ULN}$
 - AST (SGOT) $\leq 3.0 \times \text{ULN}$
 - bilirubin $\leq 2.0 \times \text{ULN}$
 - creatinine $\leq 2.0 \times \text{ULN}$.
- Written informed consent in study participation.
- Undergoing a re-biopsy prior to inclusion if tissue is accessible, which can be safely biopsied, is optional but desirable.
- Tumor evaluation has been performed within 6 weeks before date of recruitment and results are available.
- Patients must have at least one not previously irradiated lesion that can be evaluated according to RECIST version 1.1 (Eisenhauer 2009). Patients with measurable and non-measurable disease are eligible. Presence of clinically and/or radiologically documented disease.
- Age ≥ 18 years.
- ECOG Performance Status ≤ 2 .

Everolimus/Ribociclib cohort (DIVa)	Eribulin cohort (DIVb)

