4.3 Schedule

The individual study participation begins with the screening visit, consists of endocrine therapy plus everolimus/ribociclib or therapy with eribulin (depending on the treatment cohort) and ends with disease progression, the patient's death or with completion of the follow-up period. The estimated maximum duration of individual study participation is 36 months and 3 weeks both for the everolimus/ribociclib cohort and the eribulin cohort.

Patient participation is divided in 3 consecutive periods:

Pre-Treatment Evaluation Period:

Content:	Examinations and collection of data relevant to decide on patients' eligibility for further study participation. Informed consent 1
Period:	From screening to inclusion
Maximum duration:	3 weeks
Visits:	From Screening Visit to end of Inclusion Visit

Treatment Period:

Content:	Endocrine therapy combined with everolimus/ribociclib or chemotherapy with eribulin.
----------	--

Assessment of efficacy and safety data.
Informed consent 2 and 3

Period: From inclusion until disease progression or occurrence of other criteria for treatment discontinuation

Maximum duration: 12 months* (both for the everolimus/ribociclib cohort and the eribulin cohort) or until progress / death or discontinuation due to toxicities or other reasons

Visits: From Inclusion Visit to Conclusion Visit (4 weeks after last application of everolimus/eribulin)

*After treatment period the treatment with everolimus/ribociclib or eribulin can be extended if medically indicated. Patients will be followed up for toxicity and efficacy in such cases. The drug will be supplied by Novartis (everolimus/ribociclib), respectively Eisai (eribulin) on study terms for the duration of the individual study participation (including 2-year-period of follow-up assessments).

Follow-Up period:

[figure not shown]
Content: Assessment of survival, adverse events and concomitant medication. Treatment of the metastatic disease at the investigator's discretion

Period: From end of study treatment until the patient has either died or completed the 24-months follow-up period

Maximum duration: 24 months (estimation)

Visits: From Conclusion Visit of the Treatment Period to the last Follow-Up Visit

Figure 9: Clinical Trial Design

Entire Study:

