The study starts when the necessary approval has been given by the competent authority (BfArM). Furthermore the relevant ethics committee must have given a favorable opinion on study conduct before the first patient is included and consecutive all local ethical committees of the participating sites have to give their approval before the participation of one site.

The trial is terminated after the last patient has either died or completed the 24-months follow-up period.

The maximum study duration is 72 months and 3 weeks.

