8.6.2 Definition of end of the study

The study end is planned for a maximum of three years after recruitment of the last patient (LPLV). Study will be

terminated after death or complete two year follow-up off all patients. Patients will be followed for safety for 28 days after the individually last dose of everolimus/ribociclib/ eribulin study drug. At the end of the study the current progression and survival status for all patients will be updated finally and recorded in the eCRF.

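### Section 15.2 offers logistic regression for overall survival, a censored endpoint with unequal follow-up, without a fixed time point: a minor correction, but it matters for the everolimus–ribociclib comparison

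*Protocol*

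**What the plan says.** Section 1.2 defines OS as a time to death and adds that "If a patient is not known to have died, survival is censored at the date of last contact". In Section 15.2, OS is estimated by Kaplan-Meier and compared by logrank where appropriate, after which "additional multivariate analyses may be performed by suitable regression models (proportional hazard regression model, logistic regression"). For progression-free survival (PFS), the other main censored endpoint, the same section names only Cox models for covariates. The response rates have their own paragraph, which does not mention logistic regression.

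On follow-up, the synopsis gives "Maximum duration of treatment period: 12 months", and Section 4.3 sets the follow-up period as "From end of study treatment until the patient has either died or completed the 24-months follow-up period". Section 8.6.2 adds: "At the end of the study the current progression and survival status for all patients will be updated finally and recorded in the eCRF".

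Section 15.3 assigns the first 90 patients in the endocrine cohort to everolimus and the next 90 to ribociclib. Section 2.7.2 says that primary and secondary endpoints will be compared between these two groups. OS is one of the secondary endpoints.

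On status, "All analyses regarding the secondary objectives will have exploratory character only".

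**The concern.** Logistic regression has no place for a censoring time. Applied to death yes or no, it counts a patient last seen alive as a survivor and ignores how long she was observed. That is harmless only if observation time is unrelated to the factor under study, and here it can be related in two ways.

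- Under Section 4.3 the window runs 24 months past an end of treatment that falls anywhere from 0 to 12 months, so it is about 24 to 36 months long. A factor that prolongs treatment lengthens the window in which a death can be counted.
- Under the study-end update of Section 8.6.2 the window depends on calendar entry. The everolimus patients enter first and are therefore observed longer than the ribociclib patients.

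In either case the logistic result could contradict the Kaplan-Meier, logrank and Cox results from the same patients. In the second case it could show a survival advantage for ribociclib that does not exist.

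**Working it through.** The protocol gives no effect size, event count, alpha or power for any OS regression, so there is no figure to reproduce. The checks below ask what a dead/alive logistic model would do under the protocol's own follow-up rules.

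**Inputs from the protocol.** Median OS is 24–30 months or less in metastatic breast cancer (2.1) and 13.1 months with eribulin in its pivotal trial (2.7.3). A median of 9.4 months, for triple-negative patients on capecitabine (2.7.3), serves as a low bound. Median PFS is 3.7 months for eribulin (15.3), 7.8 for everolimus plus exemestane (2.7.1) and 16.0 + 9.3 = 25.3 for ribociclib plus letrozole (2.7.2). Analysed numbers are 108 and 160, with about 10% loss to follow-up (15.3). Section 4.3 states "The maximum study duration is 72 months and 3 weeks"; taking off the individual maximum of 36 months and 3 weeks leaves 36 months for recruitment.

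**Assumptions.** Exponential times, equal groups, two-sided 5% tests, uniform accrual, OS hazard ratios of 0.6–0.7 for power. There were 4,000 to 6,000 simulated trials per setting.

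**1. Factor that changes time on treatment, no OS effect, window = end of treatment + 24 months.** With PFS medians of 7.8 v 25.3 months, the proportions dead are 56.7% v 60.0% (median OS 24) and 49.0% v 52.1% (median OS 30). The odds ratios are (0.600/0.400)/(0.567/0.433) = 1.15 and (0.521/0.479)/(0.490/0.510) = 1.13, and false positives are 6.5% in both. Contrasts of 2.9 v 7.8 and 3.7 v 10 months give mean odds ratios of 1.16–1.26 and 5–8% false positives. An extreme contrast (3.2 v 25.3) reaches 13%. The time-to-event analysis stays at about 5%.

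**2. Everolimus v ribociclib, 80 v 80, recruited in months 0–18 and 18–36, no OS difference, study-end status.** At month 72 the windows are 54–72 v 36–54 months. Month 60 is the early edge (36 months of accrual plus 24), with windows of 42–60 v 24–42.

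| Status at month | Median OS | Dead, everolimus | Dead, ribociclib | Odds ratio | False positives, logistic | False positives, time-to-event |
|---|---|---|---|---|---|---|
| 72 | 24 | 80.6% | 69.6% | 0.55 | 36% | 5.4% |
| 72 | 30 | 73.6% | 61.8% | 0.58 | 36% | 4.8% |
| 60 | 24 | 73.8% | 58.3% | 0.50 | 55% | 5.0% |
| 60 | 30 | 66.3% | 50.6% | 0.52 | 51% | 5.1% |

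First row: (0.696/0.304)/(0.806/0.194) = 2.29/4.15 = 0.55. The reverse error also occurs. With everolimus truly better (hazard ratio 1/0.7 = 1.43 for ribociclib, median OS 24, month 72), the time-to-event test detects it in 52% of trials and the logistic test rejects in 5%.

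**3. Power, window = end of treatment + 24 months.**

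| Setting | Time-to-event | Logistic, dead/alive |
|---|---|---|
| n=108, median OS 13.1, OS HR 0.6, equal PFS | 0.56 | 0.49 |
| Same, PFS HR 0.6 | 0.59 | 0.42–0.46 |
| n=108, median OS 9.4, OS HR 0.6, PFS HR 0.6 | 0.64–0.66 | 0.42–0.43 |
| n=160, median OS 24, OS HR 0.6, PFS HR 0.6 | 0.62 | 0.50–0.54 |
| n=160, median OS 24, OS HR 0.7, PFS 7.8 v 25.3 | 0.34–0.38 | 0.20–0.23 |

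Ranges cover independent and correlated PFS and OS. For comparison, with one common window and a proportion p dead, the efficiency of the binary analysis relative to Cox is (1−p)·[ln(1−p)]²/p². The protocol's medians of 13.1–30 months imply p = 43–85% at 24–36 months, where a power of 0.80 falls to 0.79–0.68. It falls to 0.51 only at p = 95%.

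**4. Fixed 24-month status.** A logistic model on death by 24 months, leaving out patients censored alive before then, holds 4.2–5.6% false positives, including in the sequential comparison. Its power is about 0.49–0.53 where time-to-event gives 0.56–0.62.

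**The case against.** The text is permissive. The regression is additional, may be done, uses suitable models, and lists proportional hazards first. Kaplan-Meier and logrank remain the stated OS methods. Everything secondary is exploratory, and Section 15.2 adds that "The suitability of the statistical methods will be checked after data entry, and - if necessary - the methods will be modified accordingly". A reader could fairly take the logistic model to mean survival status at a fixed time, which is legitimate: most patients are due at least 24 months of observation, and check 4 shows that a 24-month status is sound. Choice of coding is often left to an analysis plan. This limits the consequence and the rating. It does not cure the wording: the section names the model for a censored endpoint without the time point that would make it valid, and a change after data entry would be made with the data in hand.

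The two biases also do not add up. If study-end status is used, the window no longer depends on time on treatment, and the within-cohort odds ratio returns to about 1.0. If the Section 4.3 window is used, the everolimus–ribociclib comparison falls to about 6.5% false positives. Both points stand. Which bias applies depends on which survival data are analysed.

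Stronger readings are tempting but not supported:

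- A reader might infer that the protocol itself counts censored patients as survivors. It does not say so; that is the likely default coding.
- A reader might compare exact windows of 27 and 36 months and quote odds ratios of 1.50–1.80. That requires every patient in each group to have the same window; the protocol's mixed windows give about 1.15–1.25.
- A reader might assume that OS regressions on receptor status or line of therapy are affected. Those subgroup analyses, and the specified comparison by change in tumour-cell count, are planned for PFS.

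**Conclusion.** The point holds as a minor correction. Logistic regression is named for a right-censored endpoint with unequal follow-up and with neither a time point nor a censoring rule. If it is run on dead/alive status, the error is small for within-cohort factors (odds ratio about 1.15–1.25, 5–8% false positives). It is large for the everolimus–ribociclib comparison on study-end status (about 35–55%, against 5% for a time-to-event analysis). The large figure rests on 36 months of uniform accrual, everolimus patients filling the first half, and median OS of 24–30 months.

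The loss of power is roughly 7–25 points under assumed hazard ratios of 0.6–0.7. A loss of about half might be inferred, but it appears only at the edge, such as the widest PFS contrast (0.38 to 0.20). The protocol gives no OS effect size to support it. No primary result, sample size or decision depends on this model.

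**What to change.** In the OS paragraph of Section 15.2, delete logistic regression and state that multivariable OS analyses use the proportional hazards model with the same censoring rule as the Kaplan-Meier analysis. Alternatively, restrict logistic regression to survival status at a stated time, for example 24 months, with a rule for patients censored alive before it. Keep logistic regression for the binary endpoints: tumour-cell clearance, overall response and disease control. The cost is one line of text, with no extra data, patients or visits.
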